11.1.3 Other Events of Special Interest

Hepatic Function Abnormality

Hepatic function abnormality is defined as any increase in ALT or AST to greater than 3 × ULN and concurrent increase in bilirubin to greater than 2 × ULN. Concurrent findings are those that derive from a single blood draw or from separate blood draws taken within 8 days of each other. Follow-up investigations and inquiries will be initiated promptly by the investigational site to determine whether the findings are reproducible and/or whether there is objective evidence that clearly supports causation by a disease (e.g., cholelithiasis and bile duct obstruction with distended gallbladder) or an agent other than the investigational product.

Events of hepatic function abnormality (as defined above) should be recorded according to the definitions of AE and SAE:

- If an event of hepatic function abnormality is considered to be related to a pre-existing condition and does not represent a worsening of this condition and/or is considered to be within the range of normal physiological fluctuation for the subject, the event does not meet the definition of an AE and does not need to be recorded as such.
- If a definitive diagnosis for an underlying condition unrelated to the investigational product is established for an event of hepatic function abnormality, the diagnosis should be recorded as an AE/SAE.
- If no definitive diagnosis is determined for an event of hepatic function abnormality, the term "hepatic function abnormal" should be used to report the AE/SAE.

Definition of an Overdose for This Protocol and Reporting of Overdose to Merck

For purposes of this trial, an overdose will be defined as any dose exceeding the prescribed dose for pembrolizumab by 20% over the prescribed dose. No specific information is available on the treatment of overdose of pembrolizumab. In the event of overdose, subject should be observed closely for signs of toxicity. Appropriate supportive treatment should be provided if clinically indicated. Pembrolizumab does not need to be discontinued in case of overdose, but it does need to be reported.

If an adverse event(s) is associated with ("results from") the overdose of a Merck product, the adverse event(s) is reported as a serious adverse event, even if no other seriousness criteria are met.

If a dose of Merck's product meeting the protocol definition of overdose is taken without any associated clinical symptoms or abnormal laboratory results, the overdose is reported as a non-serious Event of Clinical Interest (ECI), using the terminology "accidental or intentional overdose without adverse effect."

All reports of overdose with and without an adverse event must be reported within 5 calendar days to the MSKCC Safety Office and within 2 working days to Merck Global Safety . (Attn: Worldwide Product Safety; [contact])

12.0 CRITERIA FOR THERAPEUTIC RESPONSE/OUTCOME ASSESSMENT

For the purposes of this study, patients will be evaluated for response every 3 cycles (approximately 9 weeks), or as clincially indicated if interim toxicity occurs mandating cancer staging re-assessment. RECIST 1.1 criteria will be used.

CT scan with contrast of the chest, abdomen, and pelvis

• CT scans should be performed with contiguous cuts in slice thickness of 5 mm or less. Spiral CT should be performed using a 5-mm contiguous reconstruction algorithm.

MRI scans

MRI of the abdomen and pelvis is acceptable for measurement of lesions provided that
the same anatomical plane is used for serial assessments. If possible, the same imaging
device should be used for serial evaluations. In case of MRI, measurements will be
preferably performed in the axial (transverse) plane on contrast-enhanced T1-weighted
images. However, there are no specific sequence recommendations.

Measurability of Tumor Lesions

Tumor lesions will be categorized as follows:

- Measurable Lesions Must be accurately measured in at least one dimension (longest diameter in the plane of measurement is to be recorded) with a minimum size of:
 - 10 mm by CT scan (irrespective of scanner type) and MRI (no less than double the slice thickness and a minimum of 10 mm)
 - 10 mm caliper measurement by clinical exam (when superficial)
 - Malignant lymph nodes are considered pathologically enlarged and measurable, a lymph node must be ≥ 15 mm in short axis when assessed by CT scan (CT scan slice thickness recommended to be no greater than 5 mm).
- Nonmeasurable Lesions Nonmeasurable lesions are defined as all other lesions (or sites of disease), including small lesions (longest diameter < 10 mm or pathological lymph nodes with ≥ 10 to < 15 mm short axis). Lesions considered truly nonmeasurable include the following: leptomeningeal disease, ascites, pleural/pericardial effusion, inflammatory breast disease, lymphangitic involvement of skin or lung, abdominal masses/abdominal organomegaly identified by physical exam that is not measurable by reproducible imaging techniques.
- Target Lesions All lesions up to a maximum of 5 lesions total (and a maximum of 2 lesions per organ) representative of all involved organs should be identified as target lesions. It may be the case that, on occasion, the largest lesion does not lend itself to reproducible measurement in which circumstance the next largest lesion which can be measured reproducibly should be selected.

• **Non-target Lesions** - It is possible to record multiple nontarget lesions involving the same organ as a single item on the case record form (e.g., "multiple enlarged pelvic lymph nodes" or "multiple liver metastases")

Response Criteria

Evaluation of Target Lesions

- **Complete Response** Disappearance of all target lesions. Any pathological lymph nodes (whether target or non-target) must have reduction in short axis to < 10 mm (the sum may not be "0" if there are target nodes).
- **Partial Response** At least a 30% decrease in the sum of the diameters of target lesions, taking as reference the baseline sum diameters.
- **Progressive Disease** At least a 20% increase in the sum of diameters of target lesions, taking as reference the smallest sum on study (this includes the baseline sum if that is the smallest on study). In addition to the relative increase of 20%, the sum must also demonstrate an absolute increase of at least 5 mm. (Note: the appearance of one or more new lesions is also considered progression.)
- **Stable Disease** Neither sufficient shrinkage to qualify for PR nor sufficient increase to qualify for PD, taking as reference the smallest sum of diameters while on study.

Evaluation of Non-target Lesions

- **Complete Response** Disappearance of all non-target lesions and normalization of tumor marker level. All lymph nodes must be non-pathological in size (< 10 mm short axis).
- **Non-complete response/Non-progressive disease -** Persistence of 1 or more non-target lesion(s) and/or maintenance of tumor marker level above the normal limits.
- Progressive Disease Unequivocal progression of existing non-target lesions will be defined as the overall level of substantial worsening in non-target disease such that, even in presence of SD or PR in target disease, the overall tumor burden has increased sufficiently to merit discontinuation of therapy. In the absence of measurable disease, change in non-measurable disease comparable in magnitude to the increase that would be required to declare PD for measurable disease. Examples include an increase in a pleural effusion from "trace" to "large," an increase in lymphangitic disease from localized to widespread.

Appearance of New Lesions

The appearance of new lesions is considered PD according to RECIST v 1.1 guidelines. Considering the unique response kinetics that have been observed with immunotherapy, new lesions may not represent true disease progression. In the absence of rapid clinic al deterioration, subjects may continue to receive treatment with pembrolizumab.

Evaluation of Overall Response

Table 12 provides overall responses for all possible combinations of tumor responses in target and non-target lesions with or without the appearance of new lesions.

Table 12 Evaluation of Overall Response

Target Lesions	Non-target Lesions	New Lesions	Overall Response
Complete response	Complete response	No	Complete response
Complete response	Not evaluable	No	Partial response
Complete response	Non-complete response / non-progressive disease	No	Partial response
Partial response	Non-progressive disease and not evaluable ^a	No	Partial response
Stable disease	Non-progressive disease and not evaluable ^a	No	Stable disease
Not all evaluated	Non-progressive disease	No	Not evaluable
Progressive disease	Any	Yes/No	Progressive disease
Any	Progressive disease	Yes/No	Progressive disease
Any	Any	Yes	Progressive disease

^a Not evaluable is defined as either when no or only a subset of lesion measurements are made at an assessment.

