1.0 PROTOCOL SUMMARY AND/OR SCHEMA

Name of Investigational drug: Pembrolizumab

Title of Study: Single Arm Phase II Study to Assess the Efficacy of Pembrolizumab Plus Radiotherapy or Ablation in Metastatic Colorectal Cancer Patients

Study Centers: MSKCC

Study Period: 24 months Phase of Development: ||

Objectives:

The **primary objective** is Overall Response Rate in disease that is not ablated or radiated (Complete Response and Partial Response).

The **secondary objectives** are:

- 1. Safety and tolerability of Pembrolizumab plus radiotherapy (RT) or ablation
- 2. Overall Survival of pembrolizumab plus RT or ablation
- 3. Progression free survival rate at 1 year
- 4. Progression free survival rate at 2 years

The **exploratory objectives** are to evaluate biomarkers that may correlate with activity of pembrolizumab plus RT or pembrolizumab plus ablation in colorectal cancer (CRC), or prospectively identify CRC patients likely to respond to treatment.

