2.0 OBJECTIVES AND SCIENTIFIC AIMS

- The primary objective is Overall Response Rate in disease that is not ablated or radiated of pembrolizumab plus RT or pembrolizumab plus ablation in subjects locally advanced/metastatic CRC, according to RECIST v1.1.
- The secondary objectives are to determine:
 - o Safety and tolerability of pembrolizumab plus RT or ablation
 - o Overall Survival of pembrolizumab plus RT or ablation
 - Progression free survival rate at 1 year
 - Progression free survival rate at 2 years
- The exploratory objectives are to evaluate biomarkers that may correlate with activity of pembrolizumab plus RT or ablation in CRC, or prospectively identify CRC patients likely to respond to treatment.

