6.0 CRITERIA FOR SUBJECT ELIGIBILITY

6.1 Subject Inclusion Criteria

- 1. Be willing and able to provide written informed consent/assent for the trial.
- 2. Histologically- or cytologically- confirmed CRC.
- 3. Metastatic or recurrent CRC.

- 4. Subjects have received two or more standard available therapies known to prolong survival and for which they would be considered eligible. Such therapies should include regimens containing oxaliplatin and irinotecan in combination with a fluoropyrimidine if appropriate (e.g., FOLFOX and FOLFIRI or their variants).
- 5. At least one tumor for which palliative RT is considered appropriate standard therapy (cohort 1); or, at least one tumor for which palliative ablation is considered appropriate standard therapy (cohort 2).
- 6. At least one index lesion that will not undergo RT or ablation, and which is measurable based on RECIST 1.1.
- 7. Be ≥ 18 years of age on day of signing informed consent.
- 8. Consent for tumor biopsies and blood draws for research purposes.
- 9. Consent for use of available archived tissue for research purposes.
- 10. Have a performance status of 0 or 1 on the ECOG Performance Scale.
- 11. Demonstrate adequate organ function as defined in Table 6.1, all screening labs should be performed within 6 weeks of treatment initiation.

Table 6.1 Adequate Organ Function Laboratory Values

0	II -h
System	Laboratory Value
Hematological	
Absolute neutrophil count (ANC)	≥1,500 /mcL
Platelets	≥100,000 / mcL
Renal	
Serum creatinine	≤1.5 X upper limit of normal (ULN)
OR	OR
Measured or calculated ^a creatinine	
clearance (GFR can also be used in	≥60 mL/min for subject with creatinine levels > 1.5 X
place of creatinine or CrCl)	institutional ULN
Hepatic	
Serum total bilirubin	≤ 1.5 XULN OR
	Direct bilirubin ≤ ULN for subjects with total bilirubin levels >

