9.8.2 Research biopsy

A pre-treatment tumor biopsy will be obtained at the time of ablation or fiducial placement or during a separate procedure. On treatment biopsies will be performed 1 week (±3 days) after completing RT or undergoing ablation (from the radiated/ ablated lesion), and then 4 weeks (±1

week) after dose #1 of pembrolizumab (from a non-radiated/ ablated lesion). For patients that are unable to have biopsy 4 weeks after dose #1 of pembrolizumab, the procedure may be delayed up until Week 9.

Patients will be permitted to continue enrollment and treatment on protocol in the event that insufficient material was obtained from the biopsy. The on treatment biopsy will not be required if this is no longer considered appropriate at the time of the planned procedure, for example, if the tumor is no longer accessible or the procedure is deemed to be unsafe. Tumor lesion planned for on-treatment biopsy may be an index lesion if ≥ 2 cm in at least one diameter.

If clinically practical, subjects will undergo up to 5 core biopsies. Three core biopsies will be placed in formalin and processed for FFPE, 2 core biopsies will be immediately frozen in liquid nitrogen and then stored at -80°C (appendix B). All tissue obtained during biopsy procedures will be sent to the IMF facility for analysis under this study as indicated below. If the patient undergoes a routine procedure, tissue may be obtained for future correlative analyses. Up to 20 x 5μ m slides (unstained) may be obtained from each routine procedure where tissue was extracted. Tissue from routine procedures may be sent directly to the IMF facility for immediate processing (e.g. isolation of Tumor Infiltrating Lymphocytes).

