14.0 BIOSTATISTICS

The primary endpoint of this trial is the response rate in CRC treated with RT plus pembrolizumab (cohort 1) or ablation plus pembrolizumab (cohort 2). No response is expected in a non-radiated or non-ablated lesion with these current therapies and we consider a response rate ≤5% as unacceptable. A two-stage Simon"s optimal design will be employed to test the null hypothesis that the true response rate is ≤5% versus the alternative hypothesis that the true response rate is at least 25% with type I and II error rates of 10% each. Each cohort will be evaluated separately for this purpose. In the first stage, we will accrue 9 patients in each cohort. If 0 objective tumor responses (PR or CR) are observed among the 9 subjects treated in a cohort, then subject enrollment will be terminated in that cohort. If at least 1 response is observed among the 9 subjects treated in a cohort, then the study will be expanded to enroll a total of 24 treated subjects in that cohort. At the end of the study, if 2 or less objective tumor responses are observed in a cohort, then the study will be considered not worthy of further investigation in that particular cohort. If at the end of the study ≥3 tumor responses per RECIST 1.1 are observed in a cohort, then further investigation of pembrolizumab plus RT and/or pembrolizumab plus ablation will be considered worthwhile.

Secondary outcomes, including toxicity, the additional measures of efficacy and exploratory objectives will be summarized by cohort.

The study will complete when all subjects have either progressed or discontinued from the study for other reasons. This study requires accrual of a minimum of 18 subjects and up to a maximum of 48 subjects if both cohorts are expanded to the second stage. The accrual time is estimated to be 9 months to 2 years for both cohorts.

Antitumor Activity

Assessments of antitumor activity will be based on the ORR, PFS, and OS. Response Evaluation Criteria in Solid Tumors guidelines (v1.1) [18] with modifications to account for the unique response patterns observed with immunotherapy will be used to determine tumor response.

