The ORR is defined as the proportion of subjects CR or PR based on RECIST criteria. The exact 95% CI of ORR will be estimated using the binomial distribution. Progression-free survival will be measured from the start of treatment with pembrolizumab until the documentation of disease progression or death due to any cause, whichever occurs first. Progression-free survival will be censored on the date of last tumor assessment documenting absence of tumor progression for subjects who are still alive prior to data cutoff, dropout, or the initiation of alternate anticancer treatment. Subjects having no tumor assessments after the start of treatment with pembrolizumab will have PFS censored on the first date of treatment with pembrolizumab. Progression-free survival will be evaluated using the Kaplan-Meier method (Kaplan and Meier, 1958). Overall survival will be determined as the time from the start of

treatment with pembrolizumab until death. For subjects who are alive at the end of study or lost to follow-up, OS will be censored on the last date when subjects are known to be alive. The OS will be evaluated using the Kaplan-Meier method.

Safety and Tolerability Analyses

All recorded adverse events will be listed and tabulated by system organ class, preferred term and treatment. Any significant vital signs and clinical laboratory test results will be listed and summarized. Any significant physical examination findings, and clinical laboratory results will be listed.

Biomarker Analysis

Exploratory research studies will be done to evaluate the effect of this therapy will be performed using research blood draws and tumor biopsies at baseline, 1 week after completing RT or undergoing ablation (from the radiated/ablated lesion), and then 4 weeks after dose #1 of pembrolizumab (from a non-radiated/ablated lesion).

The pharmacodynamic effect of pembrolizumab and RT or ablation on Tumor Infiltrating Lymphocytes (TILs), such as CD4+ and CD8+ T-cells, and expression of tumor markers, such as PD-L1, will be assessed by summary statistics, and investigated graphically to explore patterns of change from pre-treatment to post-treatment specimens.

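### The target-lesion rule and the ORR definition do not exclude the irradiated or ablated lesion, so local shrinkage can be counted as a primary response

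*Combined protocol and SAP*

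**What the plan says.** Below, a treated lesion is one that is irradiated or ablated, and an untreated lesion is one that is not. All patients receive pembrolizumab.

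**Where the limit to untreated disease appears**
- Section 1.0, primary objective: "Overall Response Rate in disease that is not ablated or radiated".
- Section 2.0: "Overall Response Rate in disease that is not ablated or radiated of pembrolizumab plus RT or pembrolizumab plus ablation", assessed by RECIST v1.1.
- Section 14.0, in the sentence that sets 5% as the unacceptable rate: "No response is expected in a non-radiated or non-ablated lesion with these current therapies".
- Section 6.1, inclusion 6: "At least one index lesion that will not undergo RT or ablation, and which is measurable based on RECIST 1.1".

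**Where it does not appear**
- Section 12.0, Target Lesions, tells the reader to name as targets "All lesions up to a maximum of 5 lesions total (and a maximum of 2 lesions per organ) representative of all involved organs". Treated lesions are not excepted. Table 12 has no exception either.
- Section 14.0, decision rule: a cohort succeeds if three or more "tumor responses per RECIST 1.1 are observed in a cohort".
- Section 14.0, Antitumor Activity: "The ORR is defined as the proportion of subjects CR or PR based on RECIST criteria".

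**Related rules.** Section 8.0 places baseline imaging before radiotherapy or ablation. Section 12.0 sets PR at a fall of at least 30% in the target sum from baseline. On repeat local treatment, Section 4.2 refers to non-target lesions only, while the synopsis requires only that some target lesion is left.

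**The concern.** The objective and the null concern one quantity, and the scoring text measures another. A reader who applies Section 12.0 literally can put the treated lesion into the baseline sum, measured before it is treated, and then score a PR because that lesion shrank under local treatment. Such a response says nothing about an effect outside the treated field, and the 5% null was not set for it.

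The rules turn on very small counts, 1 of 9 to continue and 3 of 24 to succeed, and there is no control group in which the bias would show. The mixing also works the other way: a treated lesion that keeps its size dilutes the sum and can hide a real response in untreated disease. Targets are chosen at baseline, so the choice cannot be put right simply by reading later scans differently.

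**Working it through.** **1. The design as stated (Section 14.0).** Inputs: null 5%, alternative 25%, 9 patients in stage 1 (stop at 0 responses), 24 in total (succeed at 3 or more). With X(n) binomial with n patients and response rate p,

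P(declare) = P(X(24) ≥ 3) − P(X(9) = 0) × P(X(15) ≥ 3).

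- p = 0.05: 0.1159 − 0.6302 × 0.0362 = 0.0931.
- p = 0.25: 0.9602 − 0.0751 × 0.7639 = 0.9028.
- P(stop at stage 1) at p = 0.05: 0.95^9 = 0.6302.

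The stated 10% error rates are met, and a search confirms that this is the optimal design. The sample size is not at fault.

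**2. When local shrinkage alone makes a PR.** Let f be the treated lesions' share of the baseline target sum, s their proportional shrinkage and g the proportional growth of the untreated lesions. The new sum, as a share of baseline, is f(1 − s) + (1 − f)(1 + g). It is at or below 0.70 when

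s ≥ [0.30 + (1 − f)g] / f.

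| f | Example with equal targets | s needed, g = 0 | s needed, g = 10% |
|---|---|---|---|
| 50% | 1 of 2, or 2 of 4 | 60% | 70% |
| 40% | 2 of 5 | 75% | 90% |
| 33% | 1 of 3 | 90% | 110%: impossible |
| 25% or 20% | 1 of 4, or 1 of 5 | impossible | impossible |

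Below f = 30% the required shrinkage exceeds 100% even with g = 0. A new lesion or non-target progression is PD in any case.

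**3. The opposite error.** If treated lesions keep their size, untreated lesions must shrink by 0.30 / (1 − f) to score a PR: 60%, 50% or 45% at f = 50%, 40% or 33%, instead of 30%.

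**4. Effect on the decision (illustration).** The documents give no rate of local-only PRs. Suppose exactly one occurs in a cohort and every other patient responds at 5%.
- In the first 9: the chance of stopping at stage 1 goes from 63.0% to 0. P(declare) = P(X(23) ≥ 2) = 0.3206.
- In the last 15: stage 1 must still be passed, so P(declare) = P(X(23) ≥ 2) − P(X(9) = 0) × P(X(14) ≥ 2) = 0.3206 − 0.6302 × 0.1530 = 0.2242.
- At a random position: (9/24)(0.3206) + (15/24)(0.2242) = 0.2603, against 0.0931.

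**5. The same effect as a rate (also assumed).** If a share q of true non-responders is scored PR from the treated lesion, the scored rate is 0.05 + 0.95q.

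| q | Scored rate | P(declare) when the true untreated rate is 5% |
|---|---|---|
| 0 | 5.0% | 9.3% |
| 2% | 6.9% | 18.6% |
| 5% | 9.75% | 35.0% |
| 10% | 14.5% | 60.6% |
| 20% | 24.0% | 88.8% |

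**The case against.** The strongest reply is that the limit is stated, and is tied to RECIST, in the objective itself. Section 12.0 can then be read as general RECIST text subject to that objective. Sections 1.0 and 4.2 also distinguish the lesion to be treated from another measurable index lesion that will not be. This shows the intent. But Section 12.0 is the measurement instruction, no sentence excludes treated lesions from the target sum, and a guarantee of one untreated index lesion does not limit the sum to such lesions. Section 14.0 mentions RECIST modifications for immunotherapy response patterns, but Section 12.0 contains none that supplies the exclusion. Two readers acting in good faith could choose different targets.

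Several narrower points stand as limits:
- The hypothesis sentence says only true response rate; its link to untreated lesions comes from the sentence before it.
- The frequency is unknown. The treated tumor need not be measurable, it must be at least 30% of the sum, and disease elsewhere must not have progressed. In the tremelimumab study in Section 3.2, 43 of 45 evaluable patients had progressive disease. That was a different drug, but it suggests stable outside disease may be uncommon.
- Scoring a target lesion that is treated later arises under the synopsis wording, not under Section 4.2.
- Section 9.8.2 says a lesion planned for on-treatment biopsy may be an index lesion, and one such biopsy is of the treated lesion. The sentence may well mean only the untreated one, so it is weak support.

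**Conclusion.** The concern holds. The scoring rules as written do not measure the stated primary objective, and they permit a PR that reflects local treatment alone. The stated 10% type I error applies to that objective only if no such PR is counted. How far it is exceeded cannot be known from the documents: one local-only PR among 24 takes 9.3% to about 26% (22.4% to 32.1% depending on stage), and assumed rates of 2% to 10% give 18.6% to 60.6%. The shrinkage thresholds follow from the protocol's own PR rule and need no assumed rate. With only 1 of 9 and 3 of 24 needed, this should be corrected before any scan is read for the primary endpoint.

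**What to change.** - **Section 12.0.** For the primary ORR, select targets only from lesions that are neither treated nor planned for local treatment. Record treated lesions separately, and state that their shrinkage, persistence or disappearance does not determine CR or PR. State how their progression enters Table 12; one option is that unequivocal progression counts as overall PD, as for a non-target lesion.
- **Section 12.0, later local treatment.** State that if a target is treated later, its subsequent shrinkage cannot create a response. One way is to take best response only from assessments made before that treatment.
- **Section 14.0.** Define the primary ORR, and the 1-of-9 and 3-of-24 counts, as RECIST 1.1 CR or PR in untreated disease.
- **Section 9.8.2.** Say whether the index lesion that may be biopsied is the untreated one.
- **Synopsis and Section 4.2.** Reconcile their wording on which lesions may receive repeat local treatment. This review takes no position on which applies.

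The cost is a wording amendment. The sample size and decision thresholds stay as they are, and no extra scans, staff or patients are needed. Some patients will have fewer targets, so their sums will be noisier. If only assessments before later treatment of a target count, a late response in such a patient is lost.

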8.0 PRETREATMENT EVALUATION

To be completed prior to starting RT or ablation and within 6 weeks of starting pembrolizumab:

- CT scan with contrast (chest, abdomen and pelvis). If patient is unable to receive CT contrast, or the abdominal/pelvic target lesion is indeterminate on CT scan then MRI with contrast (abdomen and pelvis) plus CT chest without contrast may be perfromed. Noncontrast CT CAP may be used if the target lesion(s) do not require contrast for accurate measurements.
- 12-lead Electrocardiogram (EKG).
- Signed informed consent for study participation.
- History and physical examination, including height, weight, vital signs (temperature, pulse rate, respiration rate, blood pressure), and performance status (ECOG).
- Serum pregnancy test for all women of childbearing potential (within two weeks of starting RT or ablation). If the test result is positive related to pregnancy, the patient will not be allowed to participate in this study.
- CBC with differential and platelet count, serum chemistries (Na, Cl, BUN, Creatinine, K, CO2, and glucose), LFTs (AST, ALT, alkaline phosphatase, total bilirubin), calcium, albumin, total protein, and CEA
- Serology for HepBsAg, HepBcAb and hepatitis C antibody (negative test acceptable prior to screening period)
- Blood test for research purposes.
- Perform baseline tumor biopsy for research purposes at the time of fiducial placement or ablation or during a separate procedure.

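### Section 12 scores overall response on all disease, although the primary endpoint is response in untreated disease, so the irradiated or ablated lesion can change the primary result in either direction

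*Combined protocol and SAP*

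**What the plan says.** Sections 1.0 and 2.0 limit the primary objective to "Overall Response Rate in disease that is not ablated or radiated". Section 14.0 follows the same idea: it justifies the 5% null rate by expecting no response in a lesion that was not irradiated or ablated. Section 6.1, criterion 6, requires at least one untreated measurable index lesion.

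The response call itself is made in Section 12.0, which has no such limit:

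- On non-target disease it says "It is possible to record multiple nontarget lesions involving the same organ as a single item on the case record form", and gives multiple liver metastases as an example. No exception is made for a lesion that was irradiated or ablated.
- Non-target PD requires substantial worsening such that, "even in presence of SD or PR in target disease, the overall tumor burden has increased sufficiently to merit discontinuation of therapy".
- Table 12 gives overall PD when non-target disease progresses or when a new lesion appears, whatever the target response. No treated-site exception is stated.
- The target-lesion rule does not exclude a treated lesion either.

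The pretreatment list in Section 8.0, which includes the CT, is headed "To be completed prior to starting RT or ablation and within 6 weeks of starting pembrolizumab". The baseline therefore shows the lesion before its local treatment. Section 14.0 defines ORR as the proportion with CR or PR, without a best-response rule. It also mentions modifications of RECIST for immunotherapy but does not spell them out.

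**The concern.** Once the treated lesion is kept out of the target set, it is left among the non-target disease. Two things can then go wrong with the primary endpoint.

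First, a subject whose untreated lesions meet PR may be called PD because the treated lesion recurs or a nodule appears inside the treated site. On the stated objective that subject is a responder. Under Table 12 the subject is not.

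Second, if a treated liver lesion is pooled with untreated liver lesions in one CRF item, its shrinkage can hide growth of the untreated ones. A PR then stands although untreated disease has progressed.

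The decision rules turn on very few subjects (at least 1 of 9, then at least 3 of 24), so a single misclassified subject can settle a cohort.

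**Working it through.** **Side by side.** In every case below, the untreated target lesions meet PR.

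| Other finding | Table 12 as written | Read on untreated disease only |
|---|---|---|
| Treated lesion persists without progression | PR | PR |
| Treated lesion grows enough to meet the non-target PD bar | PD | PR |
| Nodule inside the treated site scored as a new lesion | PD | PR |
| Untreated lesions progress, but the merged item is read as non-progressive because the treated lesion shrank | PR | PD |
| New lesion outside the treated site | PD | PD |

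Rows 2 and 3 lose a responder and row 4 adds one. Rows 1 and 5 show that merging alone, or a new lesion elsewhere, does no harm to the endpoint.

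**Reproducing the design.** Inputs from Section 14.0: null rate 5%, alternative 25%, "with type I and II error rates of 10% each". "In the first stage, we will accrue 9 patients in each cohort"; a cohort stops at 0 responses, otherwise it goes to 24, and at least 3 responses count as success.

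P(success | p) = sum over x = 1 to 9 of P(X = x | 9, p) × P(Y ≥ max(0, 3 − x) | 15, p), where X and Y are the binomial response counts in stages 1 and 2.

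- p = 0.25: P(X = 1) = 0.2253, P(X = 2) = 0.3003, P(X ≥ 3) = 0.3993; P(Y ≥ 2) = 0.9198, P(Y ≥ 1) = 0.9866. Power = 0.2253 × 0.9198 + 0.3003 × 0.9866 + 0.3993 = 0.903.
- p = 0.05: the same formula gives a type I error of 0.093.
- Stop at stage 1: 0.95^9 = 0.630 under the null and 0.75^9 = 0.075 under the alternative.

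A search over alternative designs confirms that 0/9 then 2/24 is the optimal one, with an expected size under the null of 9 + (1 − 0.630) × 15 ≈ 14.5. The stated error rates are met.

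**If responders are overridden.** Let f be the share of untreated-disease responders turned into PD by the treated site. The documents give no value, so f is an assumption. The effective rate is p × (1 − f).

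| f (assumed) | Effective rate at 25% | Power | Wrong stop at stage 1 | Type I error |
|---|---|---|---|---|
| 0 | 25% | 90.3% | 7.5% | 0.093 |
| 5% | 23.75% | 88.4% | 8.7% | not computed |
| 10% | 22.5% | 86.2% | 10.1% | 0.073 |
| 20% | 20% | 80.5% | 13.4% | 0.055 |

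Power passes below 90% at f of about 0.85%, because the design has only 0.3 points of slack, and below 80% at about 21%. In expected numbers, 24 × 0.25 = 6 responders, so f = 10% is 0.6 of a responder.

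At a true rate of 25%, the chance of exactly one responder among nine is 9 × 0.25 × 0.75^8 = 22.5%. In those cohorts one overridden response would end enrolment.

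The table models the loss only. Masking of untreated progression (row 4 of the first table) works the other way, and no figure in the documents allows it to be sized.

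**The case against.** The strongest reply is that the scope is already stated in the objectives and in Section 14.0, so Section 12.0 can be read under it. That is a possible reading, but nothing in Section 12.0 tells the assessor to apply it, and Table 12 as printed gives a different answer.

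Several other points do stand:

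- The bar for non-target PD is high. One treated lesion growing while untreated targets shrink by at least 30% would seldom meet it. The new-lesion row has no such bar, although regrowth inside the treated volume may be judged the existing lesion rather than a new one.
- If best response counts, a PR recorded before the override survives, and only treated-site PD at or before the first PR scan costs a responder. The plan does not say whether best response counts.
- A nodule outside the treated volume is untreated disease, and PD is then the right call.
- Merging is permitted, not required. Scans are taken every 9 weeks and Section 16.0 keeps source documentation, so lesions could be re-read. A reader might infer that the separate readings would be lost for good; the documents do not support that.
- The error is not one-sided. The pre-procedure baseline and the open target-lesion rule could also let local shrinkage raise the response rate.

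A reader might also infer that true responders are being lost and that the trial does not have its stated power. The documents do not support this. They give no rate of treated-site failure, and the design as written reproduces its error rates.

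**Conclusion.** The primary objective and the scoring rule do not match. Section 12.0 permits misclassification of the primary endpoint in either direction through the treated lesion, and neither its frequency nor its net direction can be taken from the documents. The nominal design is sound: 90.3% power and 9.3% type I error. Power of about 88%, 86% or 80% applies only if 5%, 10% or 20% of untreated-disease responders were overridden, with no offsetting masking and no protection from an earlier PR. The same loss would lower type I error. The point is worth correcting because the decision thresholds are small and the correction is cheap. It does not show that the trial is underpowered.

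**What to change.** In Section 12.0:

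1. Record each irradiated or ablated lesion as its own CRF item, flagged as treated, never merged with other lesions and never a target lesion.
2. For the primary ORR, read the target, non-target and new-lesion columns of Table 12 on untreated disease only. Define the treated site in advance (for example, the treated volume on the first post-procedure scan), so that any new lesion outside it still counts as PD.
3. State that ORR uses best overall response.
4. Report progression at a treated site as local failure, keep it as a PFS event, and show the ordinary RECIST 1.1 overall response as a sensitivity result.

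The cost is wording in Section 12.0 and one CRF flag. There is no extra scan, and the sample size and decision rules stay the same. The one small downside is that the primary ORR may differ from ordinary RECIST in a few subjects, which is why both are shown.
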